## 17.2.2 UNSOLICITED ADVERSE EVENTS

Unsolicited adverse events are any AEs that occur any time after the vaccine/placebo is given (temporally related to study product), whether or not deemed “related” to the product, and are not solicited (specifically asked of the participant). Unsolicited AEs can be observed by study staff while the participant is at a clinic for a study visit or reported by the participant at any time. Any sign or symptom that would normally be considered a “solicited AE” (for example, fever, nausea, injection site pain) starting after 7 days post-vaccination will be recorded as an unsolicited AE.

No statistical testing will be performed for unsolicited AEs. Unsolicited AEs with a missing relationship to vaccine will not be imputed.

---

Document:	\\EEDC-NAS01A\Biosdata\Path\IVACFLU-S\IYA06804\Biostatistics		
	Documentation\SAP\IVACFLU-S-0203_SAP_Draft v1.0		
Author:	[name]	Version Number:	1.0
		Version Date:	[11AUG2017]
Template No:	CS_TP_BS016 Revision 4	Reference:	CS_WI_BS005
Effective Date:	01Apr2016		

Subject-wise listing will be presented.

The following will be presented for FA population:

1. Summary of Unsolicited Events, i.e., summary displayed for the following:
  - Total number of unsolicited AEs,
  - Subjects with at least one unsolicited AE,
  - At least one vaccine related unsolicited AE,
  - At least one serious unsolicited AE,
  - At least one severe unsolicited AE,
  - At least one life threatening unsolicited AE,
  - Subjects requiring treatment during the study,
  - Subjects with unsolicited AEs leading to withdrawal, and
  - Number of subjects died.
2. Summary of Unsolicited Adverse Events by System Organ Class and Preferred Term within Day 1 to Day 22
3. Summary of Unsolicited Adverse Events by System Organ Class and Preferred Term and severity within Day 1 to Day 22 i.e.:
  - All Adverse events are classified by severity as “Mild”, “Moderate”, “Severe” and “Life-threatening”.
  - 
  - Counts of all events will be reported and summarized, as “Any Unsolicited AE”. Percentages of subjects experiencing each reaction or event, at least one reaction or event will be calculated.
4. Summary of Unsolicited Adverse Events by System Organ Class and Preferred Term and relationship within Day 1 to Day 22
5. Summary of Unsolicited Adverse Events requiring treatment by System Organ Class and Preferred Term within Day 1 to Day 22

### 17.2.3 SERIOUS ADVERSE EVENTS

Serious adverse events (SAEs) are those events recorded as “Serious” on the Adverse Events page of the (e)CRF. A summary of serious AEs by SOC and PT will be prepared.

---

Document:	\\EEDC-NAS01A\Biosdata\Path\IVACFLU-S\IYA06804\Biostatistics		
	Documentation\SAP\IVACFLU-S-0203_SAP_Draft v1.0		
Author:	[name]	Version Number:	1.0
		Version Date:	[11AUG2017]
Template No:	CS_TP_BS016 Revision 4	Reference:	CS_WI_BS005
Effective Date:	01Apr2016		

No statistical testing will be performed for SAEs.

Subject-wise listing will be presented.

The following will be presented for FA population:

1. Summary of Serious Events, i.e., summary displayed for the following:
  - Total number of serious AEs,
  - Subjects with at least one serious AE,
  - At least one vaccine related serious AE,
  - At least one serious AE,
  - At least one severe serious AE,
  - At least one life threatening serious AE,
  - Subjects requiring treatment during the study,
  - Subjects with serious AEs leading to withdrawal, and
  - Number of subjects died.
2. Summary of serious Adverse Events by System Organ Class and Preferred Term within Day 1 to Day 91
3. Summary of serious Adverse Events by System Organ Class and Preferred Term and severity within Day 1 to Day 91 i.e.:
  - All Adverse events are classified by severity as "Mild", "Moderate", "Severe" and "Life-threatening".
  - Adverse events with missing severity will be considered as "Severe".
  - Counts of all events will be reported and summarized, as "Any Unsolicited AE". Percentages of subjects experiencing each reaction or event, at least one reaction or event will be calculated.
4. Summary of Serious Adverse Events by System Organ Class and Preferred Term and relationship within Day 1 to Day 91
5. Summary of Serious Adverse Events requiring treatment by System Organ Class and Preferred Term within Day 1 to Day 91

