### 3.2 Study Outcome Measures (Endpoints)

#### 3.2.1 Primary Endpoints

##### A. Primary Safety Endpoints, Phase 2 and 3

The number and proportion of participants reporting the following events:

- A. Solicited local adverse events, including redness / erythema, swelling / induration, pain within 30 minutes of vaccination and over a 7-day period (Days 1-7) post-vaccination.
- B. Solicited systemic adverse events, including fever, fatigue/malaise, muscle aches, joint aches, chills, nausea, vomiting, and headache within 30 minutes of vaccination and over a 7-day period (Days 1-7) post-vaccination.
- C. Unsolicited Adverse Events (AEs) occurring within 21 days post vaccination.
- D. Serious Adverse Events (SAE) occurring during the entire study period (Days 1-91).

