### **8.2.5 Final Study Visit (Day 91; $\pm$ 7)**

1. The participant will be contacted via telephone and identity confirmed.
2. Study staff will review interim medical histories and concomitant medications with the participant since these were last updated. No new concomitant medication will be recorded unless it relates to a newly identified SAE.
3. Study staff will ask about any medical event that would constitute an SAE since the last visit. No new AE information will be recorded unless it qualifies as an SAE.
4. If an SAE is reported, the clinician should record the SAE on the appropriate form, notify the entities who require notification, and refer the participant for treatment of the SAE, if warranted.

After recording the information, the participant will be discharged from the study.

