#### 10.1.1 Solicited Local and Systemic Adverse Events

- Solicited adverse events are pre-specific local and systemic adverse events that are common or known to be associated with vaccination that are actively monitored as indicators of vaccine reactogenicity. Investigators will not be required to assess causality of solicited adverse events if the onset is during the solicitation periods. If a solicited adverse event progresses beyond the solicited period, it will continue to be reported as a solicited adverse event. If the solicited adverse event occurs after the solicitation period it will be reported as an unsolicited AE.
- For this trial, solicited local and systemic AEs will be assessed by study staff 30 minutes after vaccination then daily for 7 days by the participants. Participants will be provided a thermometer, ruler and a diary to record the presence or absence of solicited AEs, severity of the solicited AE and use of concomitant medication. The severity of the solicited local and systemic adverse events will be graded using the Toxicity Table for Grading Adverse Events ([Appendix A](#)). The specific solicited local and systemic adverse events that will be reported for this trial are:
  - **Solicited local adverse event (at site of injection):**
    - Erythema / redness – based on size in cm
    - Swelling / induration (hardness at site of injection ) – based on size in cm
    - Pain

- **Systemic Reactions:**

- Fever--Body temperature
- Fatigue/malaise
- Generalized muscle aches
- Joint aches
- Chills
- Nausea
- Vomiting
- Headache

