### 10.3 AE/SAE Reporting Period and Parameter

Safety events are reported from the time of study injection (Day 1) through completion of the study at Day 91. Specifically, solicited AEs to assess local and systemic reactogenicities will be collected at 30 minutes and then daily for 7 days thereafter. If a solicited AE starts during the 7 days post vaccination period and continues beyond the 7 days it will continue to be reported as a solicited AE. SAEs will be reported from Day 1 through the end of the study at Day 91. Unsolicited AEs will be reported from Day 1 to Day 22 inclusive.

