SSRHEADD4	SSRHEADD4_C	VARCHAR2
	SSRHEADD4	VARCHAR2
	SSRHEADD4_ND	VARCHAR2
SSRHEADD5	SSRHEADD5_C	VARCHAR2
	SSRHEADD5	VARCHAR2
	SSRHEADD5_ND	VARCHAR2
SSRHEADD6	SSRHEADD6_C	VARCHAR2
	SSRHEADD6	VARCHAR2
	SSRHEADD6_ND	VARCHAR2
SSRHEADD7	SSRHEADD7_C	VARCHAR2
	SSRHEADD7	VARCHAR2

	SSRHEAD7_ND	VARCHAR2
SSRHEADONG	SSRHEADONG_C	VARCHAR2
	SSRHEADONG	VARCHAR2
	SSRHEADONG_ND	VARCHAR2
SSRHEADONG - SSRHEADSEV	SSRHEADSEV_C	VARCHAR2
	SSRHEADSEV	VARCHAR2
SSRHEADONG - SSRHEADEDAT	SSRHEADEDAT	DATE
	SSRHEADEDAT_DTS	VARCHAR2

IVACFLU-S-0203: UNSCHEDULED ASSESSMENT FORMS (UNSFM) [UNSFM]	
Unscheduled Assessment Forms [UNSFMSC]	
1.* Reason for Unscheduled visit [Reason for Unscheduled visit]	[UNSREAS] [A:3]  Physical examination [A:4]  Evaluation of health concern [A:5]  Evaluation of suspected pregnancy [A:6]  [UNSREASOTH] Other, specify A200*
2.* Unscheduled Assessment Forms [Unscheduled Assessment Forms]	[UNSFORM] [A:1]  Targeted PE [A:4]  Urine Pregnancy Test [A:6]  Anti-Influenza Serologic Assay
Key: [*] = Item is required. [✓] = Source verification required. [*] = ASCII Only Note: Source verification critical settings made in InForm will override any settings made in Central Designer.	

RDE Analytics: RD_UNSFM		
Data Variable RefName	RD Column Name	Column Data Type
UNSREAS	UNSREAS_C	VARCHAR2
	UNSREAS	VARCHAR2
	UNSREAS_ND	VARCHAR2
UNSREAS - UNSREASOTH	UNSREASOTH	VARCHAR2
UNSFORM	UNSFORM_ND	VARCHAR2
UNSFORM - Targeted PE	UNSFORM_CITMUNLIST1_C	VARCHAR2
	UNSFORM_CITMUNLIST1	VARCHAR2
UNSFORM - Urine Pregnancy Test	UNSFORM_CITMUNLIST4_C	VARCHAR2
	UNSFORM_CITMUNLIST4	VARCHAR2
UNSFORM - Anti-Influenza Serologic Assay	UNSFORM_CITMUNLIST6_C	VARCHAR2
	UNSFORM_CITMUNLIST6	VARCHAR2

IVACFLU-S-0203: LOG (LOGFM) [LOGFM]	
Log [LOGFMSC]	
1.* ✓	
Were any Unsolicited Adverse Events reported? [Were any Unsolicited Adverse Events reported?]
 
[LOGAE] [A:1]  Yes [A:2]  No If Yes, please record the details on the AEUNSOL form.

2.* ✓	
Were any Serious Adverse Events reported? [Were any Serious Adverse Events reported?]
 
[LOGSAE] [A:1]  Yes [A:2]  No If Yes, please record the details on the SAE form.

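### SAP 17.2.3 names the wrong eCRF source for SAEs: read literally, it misses serious solicited reactions from Days 1-7 and may miss SAEs after Day 22

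*Combined protocol and SAP*

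**What the plan says.** SAP 17.2.3 takes as SAEs the events marked serious "on the Adverse Events page of the (e)CRF". The same section then plans a "Summary of serious Adverse Events by System Organ Class and Preferred Term within Day 1 to Day 91", with companion tables by severity, by relationship and for events requiring treatment.

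SAEs over Days 1-91 are the fourth primary safety endpoint (Protocol 3.2.1, SAP 2.4.1.1). Protocol 10.3 gives the two kinds of event different periods: "Unsolicited AEs will be reported from Day 1 to Day 22 inclusive", whereas "SAEs will be reported from Day 1 through the end of the study at Day 91". For the Day 91 telephone contact, Protocol 8.2.5 says "No new AE information will be recorded unless it qualifies as an SAE", and sends an SAE to the appropriate form without naming it. Protocol 10.2 has SAEs recorded on an SAE form, and 10.8 requires the same for an immediate reaction that is serious.

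The annotated eCRF (version 4) has no page titled simply Adverse Events. It has an Unsolicited Adverse Event form with a *Serious?* item, and a separate repeating Serious Adverse Event form. The Log form asks about SAEs in their own question and adds: "If Yes, please record the details on the SAE form".

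On solicited reactions, Protocol 10.1.1 says: "If a solicited adverse event progresses beyond the solicited period, it will continue to be reported as a solicited adverse event".

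**The concern.** The SAP sentence points the programmer to one form when the protocol and eCRF put SAEs on another. Two kinds of event are exposed.

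The first is a serious solicited reaction with onset in Days 1-7. It is entered on the 30-minute or daily reactogenicity forms, which record size or severity but not seriousness. If it is serious it also goes on the SAE form. No text requires an entry on the unsolicited form.

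The second is an SAE with onset after Day 22, when routine reporting of unsolicited events has ended. Such an event may sit only on the SAE form.

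At stake is a primary safety endpoint whose planned claim is a zero-event statement (Protocol 13.3, SAP 17.1). One related SAE matters to that claim: in Protocol Table 16, going from 0 to 1 event in 700 moves the upper limit from 0.52% to 0.79%.

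**Working it through.** **1. The plan's own figures.** Inputs from Protocol 13.3 and SAP 17.1: 740 vaccine recipients, 5% dropout, 700 evaluable, true rates 0.33% and 0.43%.

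- Evaluable: 740 × 0.95 = 703 (stated: at least 700).
- One-sided 95% upper bound with no events: 1 − 0.05^(1/700) = 0.427% (stated: about 0.43%).
- Chance of at least one event: 1 − (1 − 0.0033)^700 = 90.1% (stated: 90%), and 1 − (1 − 0.0043)^700 = 95.1% (stated: above 95%).

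All reproduce. They presuppose that every SAE is counted.

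**2. Where each kind of SAE is recorded, and whether the SAP definition finds it.**

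| Event | Recorded on | Found by the SAP 17.2.3 definition? |
|---|---|---|
| Unsolicited SAE, Days 1-22 | Unsolicited AE form marked serious, plus SAE form | Yes |
| Solicited-type symptom starting after Day 7, serious, up to Day 22 | Unsolicited AE form (Protocol 10.1.2, SAP 17.2.2), plus SAE form | Yes |
| Solicited reaction with onset Days 1-7, serious | Reactogenicity forms (no seriousness item), plus SAE form | No |
| SAE with onset Days 23-91 | SAE form; an unsolicited AE record is possible but not required by any text | Uncertain |

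**3. The definition against the SAP's own outputs.**

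- The SAE summaries run to Day 91, and Table 14.3.1.1 counts SAEs with no time limit.
- Listing 16.2.7.5 has columns for *Serious Criteria* and *Resolved Date*, which are SAE-form items. Tables 14.3.1.1 and 14.3.4.1.5 cite that listing as a source.
- The same listing also has start and end dates, which correspond to Unsolicited AE form items. The SAE form has onset and resolved dates instead.
- SAEs requiring treatment are to be tabulated, but *Treatment Required* is an item on the Unsolicited AE form and not on the SAE form.
- The SAE severity summary in 17.2.3 is labelled *Any Unsolicited AE*, the label used in 17.2.2.

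The outputs draw on both forms, the definition names one, and no rule combines them.

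**4. Share of follow-up after Day 22.** 91 − 22 = 69 days; 69/91 = 75.8%. This is calendar time. The documents give no distribution of SAE onset.

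**5. Illustration only.** Let f be the share of related SAEs that the analysis captures. The documents give no value, so f is an assumption. The chance of at least one counted event is 1 − (1 − f·p)^700. The zero-event bound on the full Day 1-91 rate is about 0.427%/f.

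| f | p = 0.33% | p = 0.43% | Bound |
|---|---|---|---|
| 1 | 90.1% | 95.1% | 0.43% |
| 0.75 | 82.4% | 89.6% | 0.57% |
| 0.50 | 68.5% | 77.8% | 0.85% |
| 22/91 = 0.24 | 42.8% | 51.7% | 1.77% |

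The last row requires an even hazard over 91 days, loss of every SAE after Day 22 and loss of none before. It is an extreme and not an estimate.

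**The case against.** The strongest reply is that this is a loosely worded sentence in a plan whose outputs already use the right form. The Day 1-91 titles, the overview row and Listing 16.2.7.5 all point to the SAE form, and SAP 8 makes the shells the description of what will be produced. The eCRF also suggests that SAEs may be entered on the unsolicited form as well. Its *Serious?* item sends a yes answer on to the SAE form, and the Concomitant Medications form offers unsolicited AE as an indication but not SAE. On that view nothing need be lost.

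Much of this stands. A reader might infer that the unsolicited form closes at Day 22. No document says so: Day 22 is a reporting period, the form accepts any start date in 2017-2018, and Protocol 8.2.5 keeps recording open for SAEs. A reader might also infer that the form never holds solicited-type symptoms, but those starting after Day 7 belong there. Nor can one say that the SAE tables would disagree with Listing 16.2.7.5, since the visible shells cite it.

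What the reply does not cure is the definition itself. Outputs that point to the SAE form contradict the written rule, so two programmers could build different SAE datasets from this SAP. For a serious solicited reaction in Days 1-7, the literal rule has no flag to read.

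**Conclusion.** SAP 17.2.3 is wrong as written: it names an incomplete source for a primary safety endpoint and conflicts with the SAP's own SAE outputs. The gap is definite for serious solicited reactions with onset in Days 1-7 and possible for SAEs after Day 22. The conclusion rests on the eCRF version 4 forms as shown and on the absence of any rule that every SAE must also be entered on the unsolicited form.

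Its size in events cannot be stated. It would be tempting to say that three quarters of SAEs are lost. The documents do not support that: 76% is a share of days, and no loss of events is shown. It would also be wrong to say that the 0.43% figure is mistaken. It reproduces, and it stands unchanged once the SAE form is the source.

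**What to change.** Reword SAP 17.2.3 so that SAEs are all events on the SAE form with onset from Day 1 to Day 91, solicited or unsolicited, in either arm. Then:

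- Count each event once. The SAE form repeats and has initial, follow-up and final report types, so these must be collapsed.
- Reconcile SAE-form events with Unsolicited AE records marked serious before database lock, and resolve every mismatch.
- Use this source for the SAE rows of Table 14.3.1.1 and for Tables 14.3.4.1.1 to 14.3.4.1.5.
- State where *requiring treatment* comes from: a link to the Unsolicited AE record or to the concomitant medication records. An event held only on the SAE form needs the second route.
- Correct the *Any Unsolicited AE* label in the SAE severity summary.

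The cost is a short SAP revision, a modest amount of programming and one reconciliation step. No new data are needed, and the sample-size statements stay as they are.

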### 17.3 DEATHS

Listing of deaths will be provided.

---

Document:	\\EEDC-NAS01A\Biosdata\Path\IVACFLU-S\IYA06804\Biostatistics		
	Documentation\SAP\IVACFLU-S-0203_SAP_Draft v1.0		
Author:	[name]	Version Number:	1.0
		Version Date:	[11AUG2017]
Template No:	CS_TP_BS016 Revision 4	Reference:	CS_WI_BS005
Effective Date:	01Apr2016		

## 17.4 ECG EVALUATIONS

No ECG data is collected in the study.

## 17.5 VITAL SIGNS

Vital sign measurements include body temperature (oral), blood pressure (systolic and diastolic) and heart rate collected at Screening and Day 8 of the study.

The vital signs measurements, including abnormalities (grading for body temperature and blood pressure) and heart rate associated along with clinical significance (Yes/No) will be presented in the listings.

The following summaries will be provided for vital signs data:

- Actual and change from Baseline to Day 8
- Actual and change from Baseline to Day 8 by grade
- Shift from Baseline to Day 8 by grade
- Number and percentage of subjects by clinical significance
- Number and percentage of subjects shift from Baseline to Day 8 by clinical significance

## 17.6 PHYSICAL EXAMINATION

### General Physical Examinations:

Qualified study clinicians will conduct a physical examination of all participants at S1/D1. This physical examination will include the following:

- Recording of general appearance
- Physical examination of all organ systems. This includes the following:
  - neurologic examination, including cranial nerve examination
  - chest auscultation
  - examination of lymph nodes (axillary and cervical)
  - heart auscultation
  - abdomen palpation (to check for liver size)
- Measurement of the following vital signs:
  - body temperature
  - blood pressure
  - pulse/heart rate

Grade 1 elevated blood pressure (140 to < 160 mmHg systolic OR 90 to < 100 mmHg diastolic) will not be considered to be exclusionary at screening, unless judged to be clinically significant by the PI.

Document: \\IEEDC-NAS01A\Biosdata\Path\IVACFLU-S\IYA06804\Biostatistics  
Documentation\SAP\IVACFLU-S-0203\_SAP\_Draft v1.0

Author: [name]

Version Number:

1.0

Version Date:

[11AUG2017]

Template No: CS\_TP\_BS016 Revision 4  
Effective Date: 01Apr2016

Reference: CS\_WI\_BS005

### Targeted Physical Examination

The Targeted Physical Examination (PE) focuses on symptoms reported by the participant and the presence or absence of local and systemic reactogenicity. If no symptoms are reported by the participant, the Targeted PE does not need to be performed. The exam will be made by a clinician on D1 (only if D1 is on a different day from S1) and Day 8. Evaluation must be made prior to administration of injection of study product if done on Day 1.

Subject-wise listing of the data will be presented.

Summary of Shift from baseline to Day 8 by clinically significant abnormal physical examination will also be presented.

## **18. DATA NOT SUMMARIZED OR PRESENTED**

The other variables and/or domains not summarized or presented are:

- Comments
- SAE narratives

These domains and/or variables will not be summarized or presented, but will be available in the clinical study database, SDTM and/or ADaM datasets.

---

Document:	\\EEDC-NAS01A\Biosdata\Path\IVACFLU-S\IYA06804\Biostatistics		
	\Documentation\SAP\IVACFLU-S-0203_SAP_Draft v1.0		
Author:	[name]	Version Number:	1.0
		Version Date:	[11AUG2017]
Template No:	CS_TP_BS016 Revision 4	Reference:	CS_WI_BS005
Effective Date:	01Apr2016		

## APPENDIX 1

### Protocol Deviation Classifications

Categories	Severity

 
• Informed consent
 
• Eligibility and Entry Criteria
 
• Concomitant Medication Criteria
 
• Study Procedures Criteria
 
• Serious Adverse Event Criteria
 
• Randomization Criteria
 
• Visit Schedule Criteria
 
• Administrative Criteria
 
• Source Document Criteria
 
• RA or CEC Approvals Criteria
 
• IP Compliance
 
• Other Criteria
 
	
 
• Minor Deviations from accepted procedures that will not adversely affect subject/data, but should be dealt with appropriately.
 
• Major Protocol Deviation Issues that impact upon scientific, ethical, regulatory or business integrity and which, if left unattended could become critical. Such issues require timely action.
 
• Critical Protocol Deviation Issues that threaten scientific, ethical, regulatory or business integrity and could invalidate acceptability of a study (or part of it) to a customer or regulatory body, or invoke regulatory action which require immediate attention.
 

**Critical** deviations include, but are not limited to:

- Eligibility and entry criteria: subject was enrolled even though entry criteria were not satisfied
- Subject did not sign ICF yet was enrolled into the study
- Any study procedures on S1 day were done prior to consent being signed

**Major** deviations include, but are not limited to:

- Incorrect study product assigned and administered according to randomization
- Incorrect version of signed ICF (not currently approved version)
- ICF was not signed by either investigator or study participant
- IP temperature excursion (important deviation if IP is not allowed to be used, minor deviation if IP is allowed to be used)
- Subject does not complete more than 50% of subject diary card
- Subject visit (D8, D22, D91) is not completed or not done Use of prohibited drugs during study period
- SAE not reported according to protocol requirement
- Immunological sample is not collected as per protocol requirement (collected sample which cannot be analyzed is not considered as a deviation)
- Loss of source documents

**Minor** deviations include, but are not limited to:

- Subject visit is outside of visit window
- Incomplete source documents
- Procedures carried out by staff not delegated in the delegation log
- Temperature log is not maintained as per protocol requirement

Document: \\EEDC-NAS01A\Biosdata\Path\IVACFLU-S\IYA06804\Biostatistics  
Documentation\SAP\IVACFLU-S-0203\_SAP\_Draft v1.0

Author: [name]

Version Number:

1.0

Version Date:

[11AUG2017]

Template No: CS\_TP\_BS016 Revision 4  
Effective Date: 01Apr2016

Reference: CS\_WI\_BS005

## APPENDIX 2

